### **Source of Funds**

This study is funded by UAMS Department of Psychiatry.

## **Probable Duration**

The study will be completed in 1 year.

**Risks and Benefits:** 

Version #: 17, IRB #203076

PI: [name]

#### Study Intervention #1 Benefits Bupropion SR Group Bupropion SR Group Possible improvement in depression status Reasonably foreseeable risks: **Not serious** Serious Dizziness None These risks are expected to occur Agitation in more than 10 out of 100 Blurred vision subjects. Tremor Sweating Headache/migraine Inability to get adequate sleep Increased heart beat Dry mouth Constipation Decreased appetite Nausea, vomiting Weight gain **Serious Not serious** Less likely High blood pressure (Hypertension) Abnormal heart rhythm These risks are expected to occur Low blood pressure (Hypotension) in 2-9 subjects or less out of 100 Skin rash and itching subjects. Impotence Urinary frequency **Arthritis** Slowness in movement (bradykinesia) Upper respiratory complaints Fatigue Anxiety Decreased sexual desire (libido) **Serious** Rare These risks are expected to Urinary retention 1) Suicidal ideation occur in less than 1 subject in 100. 2) Suicide 3) Faint (syncope) 4) Seizures. In doses over 400mg per day, bupropion SR can be associated with seizures. The incidence of seizure with bupropion SR at the usual daily dose of 300 mg is approximately 0.1%, (or 1 out of 1000 patients), increases to approximately 0.4% at the maximum dose of 400 mg/day. The dose of 150 mg twice per week used in this study was previously shown to lead to blood levels in hemodialysis patients comparable to those obtained during routine treatment of non-hemodialysis patients treated with 300 mg daily.

Version #: 17, IRB #203076

PI: [name]

Study Intervention #2 Benefits							
Fluoxetine Group							
Fluoxetine group	Possible im	provement in depression status					
Reasonably foreseeable risks :							
	Not serious		Serious				
Likely These risks are expected to occur in more than 10 out of 100 subjects.	

Decreased app

Anxiety

Nervousness

Inability to obtasleep (insomni

	ain adequate	• None				
	Not serious		Serious				
Less likely These risks are expected to occur in 2-9 subjects or less out of 100 subjects.	• Impaired	thinking	

Alteration in blood glucose

Abnormal bleeding

Weight loss

				
			Serious				
Rare These risks are expected to occur in less than 2 subjects out of 100			
 
Suicidal ideation
 
Suicide
 
Serotonin syndrome symptoms (mental status changes [agitation], increased heart beat, change in blood pressure, dizziness, tremor, seizures, and/or nausea, vomiting, diarrhea)
 
Allergic reactions (Anaphylactoid reactions - including bronchospasm, angioedema, laryngospasm, and urticarial) and skin rash
 
				

Risks associated with stopping the study medication. To our knowledge, there are no known risks to stopping bupropion abruptly. In addition, although abrupt termination of selective serotonin reuptake inhibitors (SSRIs) have been associated with a SSRI discontinuation syndrome (consisting of symptoms described as "head shocks," dizziness, electric shock-like sensations, sweating, nausea, insomnia, tremor, confusion, nightmares, and vertigo), fluoxetine has been associated with only mild dizziness and vertigo in patients maintained on fluoxetine at 20 mg/day that was abruptly terminated in a randomized double blind trial (141).

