#### Choices of bupropion and fluoxetine for the treatment:

Bupropion is unique amongst antidepressants because it selectively blocks reuptake of NE and DA without having appreciable affinity for postsynaptic receptors including histamine, α- or β-adrenergic, 5-HT, or acetylcholine [30, 88]. This confers a favorable side effect and safety profile [89], absence of weight gain [90] or somnolence [91]; side effects frequently reported by HD patients with other antidepressants [92-95]. Bupropion has no clinically significant effects on the cardiovascular system (e.g., heart rate, blood pressure, QTc interval) in patients with MDD [96]. It can increase the incidence of seizures [97] in a dose-dependent (>450 mg/day) [30] fashion in patients with a history of seizures; therefore it is contraindicated in these patients. Bupropion may preferentially reduce a subset of symptoms of MDD common in medically ill patients, including fatigue, drowsiness, cognitive dysfunction, anhedonia, and mental concentration [98, 99]. In healthy humans, after oral administration, bupropion is rapidly and ~100% absorbed by the intestine, metabolized in the liver, and excreted via kidney. The hepatic cytochrome P450 (CYP) 2B6 catalyzes bupropion to a primary active metabolite, hydroxylbupropion. Several studies [62, 100, 101] have provided guidelines and recommendations about antidepressant agents in patients with ESRD/HD. One study [80] determined the PK of bupropion and its active metabolites in HD patients following a single 150-mg oral dose and found comparable PK profile to individuals with normal renal function. Compared with controls, hydroxyl-bupropion demonstrated a >2fold greater AUC and substantially increased t1/2, indicating reduced clearance. Based on these data, the authors [80] suggested an oral dose of 150 mg bupropion every 3 days in HD patients.

While it has been suggested that antidepressants may in general reduce inflammation, research data suggests that SSRIs and tricyclic antidepressants may not. Other hand, there has been considerable recent interest in the anti-inflammatory effects of bupropion, although more research is needed [102]. Brustolim et al. [33] demonstrated that bupropion significantly reduced the levels of TNF- $\alpha$  in mice challenged with lipopolysaccharide and suggested that this effect might have important clinical consequences. In case reports, Kast and Altschuler [35, 36] proposed the potential anti-inflammatory

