Participation of an eligible subject in this clinical trial is a voluntary process. Subjects will not be coerced or influenced by the study personnel. In order to participate, subjects will have to voluntarily initiate a phone screening and subsequently come to a face-to-face consent/initial evaluation meeting. A research staff member or study investigator will conduct the consent process in order to minimize the possibility of undue influence from the treating physician on their hemodialysis team. Subjects will be informed that participation is voluntary and not participating will not affect the delivery of the routine health care. They and their treating physicians will be informed that the medications being used in the current study are routinely available and relatively inexpensive to obtain. They do not have to participate in this study to receive any of the treatment options.

Subjects are randomly assigned to open label treatment with one of two medications. Therefore, there are two groups:

- Bupropion group:
  - For patient not on hemodialysis, oral administration of bupropion SR tablet at a dose of 150 mg daily. Bupropion SR doses will be adjusted upward or downward based on tolerability and response.
  - For patient on hemodialysis or peritoneal dialysis, oral administration of bupropion SR tablet at a dose of 150 mg on the 1st and the 3rd dialysis day of each week. Bupropion SR doses will be adjusted upward or downward based on tolerability and response.
- Fluoxetine group: Oral administration of fluoxetine tablet will be started at a dose of 10 mg/day for the first week and then increased, as tolerated to 20 mg/day for weeks 2–4. After this, doses will be adjusted based on clinical response and side effects up to a maximum dose of 60 mg/daily by week 10.

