## 6. Research Plan

The current study proposes to recruit up to 50 participants in order to have 40 completers. Eligible CKD patients with MDD will be randomly assigned to 12 weeks of open label, flexible dose treatment with either Bupropion SR (N=20) or Fluoxetine (N=20). Patients will be recruited from the UAMS dialysis center or other local dialysis centers via flyers, referral by their treating physician and/or newspaper ads. Written consent will be obtained before any study procedures. Subjects are randomly assigned to open label treatment with one of the following:

• Bupropion group:

Version #: 17, IRB #203076

PI: [name]

 For patient not on hemodialysis or peritoneal, oral administration of bupropion SR tablet at a dose of 150 mg daily. Bupropion SR doses will be adjusted upward or downward based on tolerability and response.

- For patient on hemodialysis or peritoneal dialysis, oral administration of bupropion SR tablet at a dose of 150 mg on the 1st and the 3rd dialysis day of each week. Bupropion SR doses will be adjusted upward or downward based on tolerability and response.
- Fluoxetine group: Oral administration of fluoxetine tablet will be started at a dose of 10 mg/day for the
  first week and then increased, as tolerated to 20 mg/day for weeks 2–4. After this, doses will be
  adjusted based on clinical response and side effects up to a maximum dose of 60 mg/daily by week
  10.

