Participants will receive the study medication during the baseline assessment and instructed to begin the medication on day 1 (1st dialysis day) of week 1 of the study. For patient on hemodialysis or peritoneal dialysis, generic bupropion SR will be dosed at 150 mg on the 1st and the 3rd dialysis day of each week with doses adjusted upward or downward based on tolerability. The initial dose of bupropion-SR is based on the findings of Worrall et al [80], who measured plasma bupropion levels in a pharmacokinetic study of bupropion in HD patients. For patient not on hemodialysis or peritoneal dialysis, generic bupropion SR tablet will be dosed at 150 mg daily. Bupropion SR doses will be adjusted upward or downward based on tolerability and response. Fluoxetine will be started at 10 mg/day for the first week and then increased, as tolerated to 20 mg/day for weeks 2–4. After this, doses will be adjusted based on clinical response and side effects up to a maximum dose of 60 mg/daily by week 10 [62]. At the week 12 visit, the participants will stop the medication or may undergo a 1-2 week taper (depending on maintenance dose) if they are on a dose of fluoxetine that is higher than 20 mg.

Subjects will be seen during weeks 1, 2, 3, 4, 6, 8, 10, and 12 in face-to-face meetings by a rater blind to study medication and a study physician for Ham-D ratings, CGI, medication accountability, and measurement of adverse events. On weeks 5, 7, 9 and 11, subjects will come in to return the previous week's pill bottles and pick up the current week's medication. Table 1 shows study procedures. Medication will be prepared by UAMS Research Pharmacy, labeled with the directions for use and contact information, and given to participants by study staff on a weekly basis. Compliance will be monitored using the MAFV at each scheduled encounter and by analysis of antidepressant blood levels. Results of a second EKG done during week 4 will be reviewed to ensure QTc interval is less than 500 msec.

In order to control for the potential confound of chronic pain we will characterize it with the physical and psychological pain scale and with two objective measures, i.e. the pressure pain threshold and the Quantitative Sensory Test (QST).

Version #: 17, IRB #203076

PI: [name]

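### Bupropion SR may be titrated upward with no maximum in any dosing rule, although the risk text refers to a maximum of 400 mg/day and no equivalent is given for dialysis patients

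*Combined protocol and SAP*

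**What the plan says.** **Dosing rules.** Section 5 (Consent Process) and Section 6 (Research Plan) start patients who are not on dialysis with "oral administration of bupropion SR tablet at a dose of 150 mg daily". Patients on hemodialysis or peritoneal dialysis start at 150 mg on two dialysis days a week. For both groups the treatment lists add "Bupropion SR doses will be adjusted upward or downward based on tolerability and response". The later dosing paragraph of Section 6 gives the dialysis rule a second time, "with doses adjusted upward or downward based on tolerability", without mentioning response. None of these places gives a step size or a highest dose for bupropion. The fluoxetine rule beside them has a starting dose, a schedule and a top dose of 60 mg/day by week 10.

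**Risk statements.** The Bupropion SR Group table under Risks and Benefits lists seizure among the rare serious risks and states "In doses over 400mg per day, bupropion SR can be associated with seizures". It then puts incidence at about 0.1% for 300 mg daily, which "increases to approximately 0.4% at the maximum dose of 400 mg/day". It also says that 150 mg twice weekly gave hemodialysis patients blood levels comparable to 300 mg daily in patients not on hemodialysis.

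**Background.** Section 2, under the choice of the two drugs, says that bupropion can raise seizure incidence "in a dose-dependent (>450 mg/day) [30] fashion in patients with a history of seizures". It names no formulation there. The Exclusion Criteria in Section 4 rule out anyone who has ever had a seizure.

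**The concern.** The protocol names a maximum bupropion dose where it describes risk, but the instructions that staff follow when adjusting the dose do not contain it. A titration that obeys the dosing text can therefore go above the protocol's own figure. The gap is in one arm only, since fluoxetine has its limit in the same paragraphs.

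For dialysis patients, copying the 400 mg/day figure across would not close the gap. They are dosed by the week, and the risk text itself says that a small weekly dose gives them levels comparable to a much larger daily dose in other patients.

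What is at stake is patient safety on a risk that the protocol lists as serious, and consistent dosing within the arm. The power calculation and the primary analysis are not affected.

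**Working it through.** No design figure needs reproducing here. The check compares the dose statements and does the arithmetic that they imply.

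**1. Is there a limit anywhere in the operating text?** Sections 5 and 6 give none for bupropion. Procedures to Minimize Risks has a fluoxetine taper but no bupropion dose limit. Drug levels are taken at weeks 4 and 12 (Biochemical Measurements), and Section 6 uses them to monitor compliance. The 400 mg/day maximum appears once, in a sentence about incidence.

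**2. Patients not on dialysis.** Start: 150 mg/day. The step size is not stated; assume 150 mg, the only bupropion SR dose the rules name.
- One step: 150 + 150 = 300 mg/day, below both figures.
- Two steps: 150 + 2 × 150 = 450 mg/day, above 400 but not above 450.
- Three steps: 150 + 3 × 150 = 600 mg/day, above both.

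The result does not hinge on that step. Physician visits before week 12 fall at weeks 1, 2, 3, 4, 6, 8 and 10, which is seven occasions. With an equal increase at each, any step above (400 − 150)/7 ≈ 36 mg passes 400 mg/day by week 10. Any step above (450 − 150)/7 ≈ 43 mg passes 450 mg/day.

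**3. Hemodialysis patients.** Start: 2 × 150 = 300 mg/week, or 300/7 ≈ 43 mg/day, far below any literal mg/day figure. The risk text equates this with 300 mg daily off dialysis, which is 7 × 300 = 2,100 mg/week. The factor is 2,100/300 = 7.
- One added weekly dose: 3 × 150 = 450 mg/week. If levels are proportional to dose, this corresponds to 450 × 7 = 3,150 mg/week off dialysis, or 450 mg/day. That is above 400 and equal to 450.
- Two added weekly doses: 600 mg/week, corresponding to 600 mg/day.

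Proportionality is an assumption. The added dose raises the weekly amount by 50%. If levels rise by a fraction k of that, the equivalent is 300 × (1 + 0.5k) mg/day: 300 at k = 0, 400 at k = 2/3 and 450 at k = 1. The equivalence is stated for hemodialysis only; the documents give none for peritoneal dialysis.

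**4. The seizure statements side by side.**
- Risk text, first statement: SR, above 400 mg/day, any patient.
- Risk text, second statement: SR, about 0.1% at 300 mg and 0.4% at 400 mg, so seizures are reported at and below the level that the first statement presents as the threshold.
- Background: formulation not named, above 450 mg/day, patients with a seizure history.

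**5. Size in events.** With 20 patients in the arm, the chance of at least one seizure is 1 − (1 − p)^20. At p = 0.001 this is 2.0% (20 × 0.001 = 0.02 expected events). At p = 0.004 it is 7.7% (0.08 expected). Both assume that every patient receives the dose in question. The documents give no incidence above 400 mg/day, so the risk in the range left open cannot be computed from them.

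**The case against.** The best defence is that titration is supervised. Upward adjustment depends on tolerability, a study physician sees patients at weeks 1, 2, 3, 4, 6, 8, 10 and 12, medication is dispensed weekly, and adverse events are reviewed each week. A reader of the whole protocol also meets the 400 mg/day maximum. This makes runaway dosing unlikely, and nothing suggests that high doses are intended. But none of these safeguards is a dose limit, and none refers to the figure in the risk text.

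Four stronger readings are tempting, and the documents do not support them:
- **The 400 and 450 mg/day figures contradict each other.** They are not like for like. One is for SR without restriction on patients. The other names no formulation and concerns people who cannot enrol. Both could be true. What remains is that the Background text, read alone, suggests the dose-related risk lies outside the trial population, and the risk table does not say so.
- **The protocol names no maximum at all.** It does, but only in the risk text.
- **The fourfold rise from 0.1% to 0.4% measures the danger of the missing limit.** That rise lies between 300 and 400 mg/day, wholly within the stated maximum, and says nothing about exceeding it.
- **Slowly cleared drug and literal mg/day thresholds meet in the same patients.** The reduced clearance of the active metabolite is reported for hemodialysis patients, whose starting dose averages about 43 mg/day. For them the argument must run through the blood-level equivalence, as in step 3 of the working.

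**Conclusion.** The point holds as an unreconciled gap between the dosing rules and the risk text. The rules permit bupropion SR doses above the only maximum that the protocol mentions. Off dialysis this takes two assumed 150 mg steps. In hemodialysis patients one added weekly dose corresponds to about 450 mg/day if levels are proportional to dose, and passes 400 if levels rise by more than two thirds of what proportionality predicts. The risk text also needs correcting within itself.

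Absolute seizure risk at the doses for which the protocol gives figures is small. The documents neither quantify risk above them nor show that such doses are planned. The point should be settled because seizure is a listed serious risk and the correction is simple.

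**What to change.** Reconcile the bupropion dosing rules in Sections 5 and 6 (both the treatment lists and the dosing paragraph of Section 6) with the seizure statements in Section 2 and in Risks and Benefits. Do this separately for patients on and off dialysis, and express the dialysis rule in terms that fit weekly dosing and the stated blood-level equivalence. Make the two versions of the dialysis adjustment rule agree on whether response counts. Reword the risk text so that its threshold sentence and its incidence figures are consistent, and say in Section 2 how the figure for patients with a seizure history relates to a trial that excludes them. Any limit is for the sponsor's clinicians to set; none is proposed here. The cost is a wording amendment, with no change to sample size, visits or analysis.

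### Bupropion SR may be titrated upward with no stated maximum or step, and the protocol does not settle where titration in hemodialysis patients should stop

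*Combined protocol and SAP*

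**What the plan says.** **Dosing.** Section 5 (Consent Process) and section 6 (Research Plan) start dialysis patients on 150 mg of bupropion SR twice a week: "generic bupropion SR will be dosed at 150 mg on the 1st and the 3rd dialysis day of each week with doses adjusted upward"; reductions are allowed too. Patients not on dialysis start on 150 mg every day: "For patient not on hemodialysis or peritoneal, oral administration of bupropion SR tablet at a dose of 150 mg daily". The titration rule is "Bupropion SR doses will be adjusted upward or downward based on tolerability and response". One sentence in section 6, on dialysis patients, names tolerability only. No maximum, step or schedule is given for bupropion. For fluoxetine the same sections give a starting dose, a first step and a ceiling: "doses will be adjusted based on clinical response and side effects up to a maximum dose of 60 mg/daily by week 10".

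**Seizure risk.** The bupropion table under Risks and Benefits says "In doses over 400mg per day, bupropion SR can be associated with seizures". It puts the incidence at about 0.1% at 300 mg daily, which "increases to approximately 0.4% at the maximum dose of 400 mg/day". The Background (Choices of bupropion and fluoxetine) gives a different threshold, above 450 mg/day, and ties it to patients with a seizure history, whom section 4 excludes.

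**Dialysis conversion.** The risk table then says "The dose of 150 mg twice per week used in this study was previously shown to lead to blood levels in hemodialysis patients". It describes these levels as comparable with the ones seen off hemodialysis at 300 mg a day. No source is cited there. Section 6 bases the starting dose on a pharmacokinetic study that the reference list titles as single-dose. The Background reports from it a bupropion profile comparable to normal renal function, a hydroxybupropion AUC more than twice that of controls, and a suggested dose of 150 mg every 3 days.

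**The concern.** The drug whose seizure risk the protocol itself describes as dose-dependent is the one without a ceiling. An investigator with a non-responding dialysis patient may raise the dose and finds no rule for how far. The risk table holds the only conversion from dialysis dosing to the usual daily doses on which the seizure rates rest. Taken at its word, it leaves almost no room above the starting dose. If it is not right, the risk text relies on an unsupported statement. Either way the stopping point is unclear. The stake is patient safety and the accuracy of the risk information, not the efficacy analysis.

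**Working it through.** **Inputs.** Dialysis start: 150 mg × 2 = 300 mg/week (sections 5 and 6). Stated equivalent: 300 mg/day in patients not on hemodialysis, with 400 mg/day called the maximum (risk table). Background: metabolite AUC ratio above 2, suggested dose 150 mg every 3 days, threshold above 450 mg/day. Assumptions of this check: exposure proportional to dose, and a titration step of 150 mg, the only bupropion tablet dose the protocol names.

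**1. What the comparability sentence requires.** Usual dosing is 300 × 7 = 2100 mg/week. Exposure per mg relative to normal is then r = 2100 / 300 = 7. The documents do not allow this figure to be reproduced. A single-dose metabolite ratio above 2 is a lower bound, so it neither confirms 7 nor excludes it.

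**2. One added tablet a week.** The weekly dose becomes 300 + 150 = 450 mg. Daily equivalent = weekly dose / 7 × r. The weekly dose that matches 400 mg/day is 400 × 7 / r = 2800 / r.

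| r | 300 mg/week (start), mg/day | 450 mg/week, mg/day | Weekly dose matching 400 mg/day, mg |
|---|---|---|---|
| 2 | 86 | 129 | 1400 |
| 3 | 129 | 193 | 933 |
| 4 | 171 | 257 | 700 |
| 7 | 300 | 450 | 400 |

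The 450 mg week passes 400 mg/day only when r exceeds 2800 / 450 = 6.2. At r = 7 it is above the risk table's 400 and equal to the Background's 450.

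**3. Against the suggested dose.** 150 mg every 3 days averages 150 × 7 / 3 = 350 mg/week. The start of 300 mg is below this; 450 mg is 450 / 350 = 1.29 times it.

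**4. Expected seizures.** This takes 20 to 25 bupropion patients (40 completers or 50 enrolled, split equally), all at the stated dose.
- At 300 mg/day: 20 × 0.001 = 0.02 to 25 × 0.001 = 0.025.
- At 400 mg/day: 20 × 0.004 = 0.08 to 25 × 0.004 = 0.10.

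The documents give no rate above 400 mg/day.

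**5. Search for a ceiling elsewhere.** Drug levels are drawn at weeks 4 and 12. Section 6 describes them as a compliance check, and no rule links them to dose. Prior seizure or stroke is an exclusion, which lowers risk but does not limit dose. Neither adverse event review nor physician withdrawal sets a maximum.

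**The case against.** The best reply is that the 450 mg/day figure depends on the very sentence whose support is questioned, and on two assumptions the protocol does not state. Comparable also does not mean equal. If 150 mg twice weekly matched about 267 mg/day instead of 300, the third tablet would only reach 400 (267 × 450 / 300). At ratios of 2 to 4 the same dose is well inside the usual range. That stands, so the figure is conditional and shows only what the protocol's own conversion would mean.

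There are also real safeguards. The dialysis start is below the suggested 350 mg/week. Medication is dispensed weekly. A physician sees patients at eight visits, with a structured adverse event inquiry at each, and the investigators review events weekly. The non-dialysis start of 150 mg daily is half the 300 mg that the risk table calls usual. These reduce the practical risk, but none tells an investigator where to stop, and a seizure can be the first sign that a dose is not tolerated.

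It may also be said that the 400 mg/day in the risk table is already the cap. It appears there as seizure information, not as a dosing rule. A reader might go further and carry 400 mg/day over as a literal limit in dialysis patients. The documents do not support that, because the next sentence of the table gives hemodialysis its own conversion.

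**Conclusion.** The omission is certain and needs no pharmacokinetic assumption: bupropion SR has no maximum and no step, while fluoxetine has both a first step and a cap. What makes it more than missing detail is that the first 150 mg increase the rule permits would reach about 450 mg/day-equivalent under the protocol's own hemodialysis conversion. That size rests on r = 7, dose proportionality and a 150 mg step. Over r = 2 to 7 the range is 129 to 450 mg/day, and the weekly dose matching 400 mg/day runs from 1400 down to 400 mg.

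Two stronger readings are not supported. A reader might conclude that the comparability sentence is wrong; it is uncited and unverified, but nothing in the documents disproves it. A reader might also apply the hemodialysis ratio to peritoneal dialysis patients, or to undialysed patients with low eGFR, and calculate very large equivalents for them. The documents give no exposure ratio for either group. For undialysed patients the supportable point is narrower: eligibility has no lower eGFR limit, and their dose has no ceiling either.

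The expected number of seizures is well below one, and no planned efficacy analysis changes. The correction is still worth making, because it is cheap and concerns a serious risk.

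**What to change.** - **Dosing text, sections 5 and 6.** State a maximum bupropion SR dose and a step size wherever the dosing is described. For dialysis patients, express it per week and name the source. The only suggested hemodialysis dose summarised in the documents averages 350 mg/week; under the risk table's conversion the ceiling is 400 mg/week. For patients not on dialysis, express it per day, not above 400 mg/day, with the sponsor setting any lower limit for low eGFR from a cited source.
- **Risk table.** Cite a multiple-dose source for the comparability sentence, or soften or delete it.
- **Thresholds.** Reconcile 400 mg/day in the risk table with 450 mg/day in the Background.

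**Cost.** A clause in each dosing description and a few words of risk and background text, with no change to sample size, visits or analyses. The real price is flexibility: under either weekly figure a third 150 mg tablet does not fit, so dialysis patients could rise little above the start while fluoxetine can go to 60 mg/day. The sponsor should make that clinical choice knowingly and bear it in mind when comparing the drugs under Aim 2.
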